8.3 Adverse events

The definitions of an AE and SAE can be found in Appendix 3 (Section 10.3).

Adverse events will be reported by the participant (or, when appropriate, by a caregiver, surrogate, or the participant's legally authorized representative).

The investigator and any designees are responsible for detecting, documenting, and recording events that meet the definition of an AE or SAE and remain responsible for following up AEs that are serious, considered related to CZP or study procedures, or that caused the participant to discontinue the study (see Section 7).

8.3.1 Time period and frequency for collecting AE and SAE information

All AEs and SAEs will be collected from the signing of the ICF until the SFU visit at the time points specified in the Schedule of Activities (Section 1.3).

In order to ensure complete safety data collection, all AEs occurring during the study (ie, after the signing of the ICF), including any pretreatment and posttreatment periods required by the protocol, must be reported in the eCRF. This includes all AEs not present prior to the initial visit and all AEs that recurred or worsened after the initial visit.

All SAEs will be recorded and reported to the Sponsor or designee within 24 hours, as indicated in Appendix 3 (Section 10.3). The investigator will submit any updated SAE data to the Sponsor within 24 hours of it being available.

The investigator is specifically requested to collect and report to UCB (or its representative) any SAEs (even if the investigator is certain that they are in no way associated with CZP), up to 35 days (± 5 days) after the final blood sample is obtained for each participant, and to also inform participants of the need to inform the investigator of any SAE within this period. Serious AEs that the investigator thinks may be associated with CZP must be reported to UCB, regardless of the time between the event and the end of the study.

The method of recording, evaluating, and assessing causality of AEs and SAEs and the procedures for completing and transmitting SAE reports are provided in Appendix 3 (Section 10.3).

8.3.2 Method of detecting AEs and SAEs

Care will be taken not to introduce bias when detecting AEs and/or SAEs. Open-ended and nonleading verbal questioning of the participant is the preferred method to inquire about AE occurrences.

8.3.3 Follow-up of AEs and SAEs

After the initial AE/SAE report, the investigator is required to proactively follow each participant at subsequent visits/contacts. All SAEs, and nonserious AEs of special interest (as defined in Section 8.3.6), will be followed until resolution, stabilization, the investigator determines that it is no longer clinically significant, the event is otherwise explained, or the participant is lost to follow up (as defined in Section 7.3). Further information on follow-up procedures is given in Appendix 3 (Section 10.3).

8.3.4 Regulatory reporting requirements for SAEs

Prompt notification by the investigator to the Sponsor of an SAE is essential so that legal obligations and ethical responsibilities towards the safety of participants and the safety of CZP under clinical investigation are met.

The Sponsor has a legal responsibility to notify both the local regulatory authority and other regulatory agencies about the safety of CZP under clinical investigation. The Sponsor will comply with country-specific regulatory requirements relating to safety reporting to the regulatory authority, IRB/IEC, and investigators.

Investigator safety reports must be prepared for suspected unexpected serious adverse reactions according to local regulatory requirements and Sponsor policy and forwarded to investigators as necessary.

An investigator who receives an investigator safety report describing a SAE or other specific safety information (eg, summary or listing of SAEs) from the Sponsor will review and then file it along with the IB and will notify the IRB/IEC, if appropriate according to local requirements.

8.3.5 Pregnancy

Details of the pregnancies for all study participants will be collected from enrollment into the study and up to the SFU. UCB standing guidance for collection of data pertaining to pregnancy and pregnancy outcomes will be used during this study for the collection of such data (Section 8.2.5). Information regarding collection of pregnancy-related data is located in Appendix 4 Section 10.4.

Abnormal pregnancy outcomes (eg, spontaneous abortion, fetal death, stillbirth, congenital anomalies, and ectopic pregnancy) are considered SAEs.

8.3.6 Adverse events of special interest

An AE of special interest is any AE that a regulatory authority has mandated to be reported on an expedited basis, regardless of the seriousness, expectedness, or relatedness of the AE to the administration of a UCB product/compound.

For CZP, the following events require immediate reporting (within 24 hours regardless of seriousness) to UCB:

- Hy's Law
 - Potential Hy's Law, defined as $\geq 3x$ upper limit of normal (ULN) alanine aminotransferase or aspartate aminotransferase with coexisting $\geq 2x$ ULN total bilirubin in the absence of $\geq 2x$ ULN alkaline phosphatase, with no alternative explanation for the biochemical abnormality (ie, without waiting for any additional etiologic investigations to have been concluded). Follow-up information should then be reported if an alternative etiology is identified during investigation and monitoring of the participant.
- Serious infections including opportunistic infections
- Malignancies including lymphoma
- Congestive heart failure
- Demyelinating-like disorders
- Aplastic anemia, pancytopenia, thrombocytopenia, neutropenia, and leucopenia
- Serious bleeding events
- Lupus and lupus-like syndrome
- Serious skin reactions (eg, Stevens Johnson Syndrome, toxic epidermal necrosis, and erythema multiforme).

8.3.7 Disease-related events and/or disease-related outcomes not qualifying as AEs or SAEs

Anticipated SAEs are anticipated to occur in the population studied in this protocol at some frequency that is independent of drug exposure. A summary of anticipated SAEs is presented in [Table 8-1](#) (Appendix 3).

This list does not change the investigator's obligation to report all SAEs (including Anticipated SAEs) as detailed in [Section 8.3.1](#) and [Section 10.3](#) (Appendix 3).

Table 8-1: Anticipated SAEs

Population	Anticipated SAE(s)
Rheumatoid arthritis	Rheumatoid arthritis
Crohn's disease	Crohn's disease Perianal abscess Abdominal pain
Ankylosing spondylitis	Ankylosing spondylitis
Psoriatic arthritis	Psoriatic arthritis
Plaque psoriasis	Plaque psoriasis

SAE=serious adverse event

8.4 Safety signal detection

Selected data from this study will be reviewed periodically to detect as early as possible any safety concern(s) related to CZP so that investigators, clinical study participants, regulatory authorities, and IRBs/IECs will be informed appropriately and as early as possible.

The Study Physician or medically qualified designee/equivalent will conduct an ongoing review of SAEs and perform ongoing SAE reconciliations in collaboration with the Patient Safety representative.

As appropriate for the stage of development and accumulated experience with CZP, medically qualified personnel at UCB may identify additional safety measures (eg, AEs, vital signs) for which data will be periodically reviewed during the course of the study.

8.5 Treatment of overdose

Excessive dosing (beyond that prescribed per the local label) will be recorded by the study participant in the diary and also recorded in the eCRF. The dosing documentation will be reviewed and verified by the investigator and/or home health nurse. Any SAE or nonserious AE associated with excessive dosing must be followed as any other SAE or nonserious AE.

Overdose events are only considered AEs or SAEs if there are associated clinical signs and symptoms or if the act of taking the excess CZP itself is an AE or SAE (eg, suicide attempt).

UCB does not recommend specific treatment for an overdose. In the event of an overdose, the treating physician should:

1. Contact the Medical Monitor immediately.
2. Closely monitor the participant for any AE/SAE and laboratory abnormalities until commercial CZP can no longer be detected systemically (at least 70 days).
3. Obtain a plasma sample for PK analysis within 70 days from the date of the last dose of commercial CZP if requested by the Medical Monitor (determined on a case-by-case basis).
4. Document the quantity of the excess dose as well as the duration of the overdose in the eCRF.

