 - Pregnancy Period: PK samples will be collected prior to the subsequent dose (predose) every 4 weeks (Q4W) starting with the first dose after enrollment. Further, postdose (7 ± 1 day after dose administration) PK samples will be collected every 8 weeks (Q8W) throughout the pregnancy. It is expected that there will be approximately 6 predose and 3 postdose PK samples collected per study participant (if there are no discontinuations) over the pregnancy.
 - Postpartum Period: A predose sample 12 weeks (± 1 week) postpartum will be collected during the Postpartum Period. If possible, 1 additional postdose sample 1 week (± 1 day) after the 12 weeks postpartum dose will also be collected.
- Safety Follow-up contact: All study participants will be contacted via telephone for a SFU 5 weeks (± 5 days) after final study visit.

If any participant withdraws early, she will complete the SFU contact.

The end of the study is defined as the date of the SFU/last contact of the last participant in the study.

Number of participants:

Approximately 25 to 30 participants are planned to be screened to achieve approximately 20 enrolled study participants (ie, study participants who have provided the first blood sample). Enrollment will occur until a minimum of 10 study participants have longitudinal data (defined as at least 4 quantifiable predose and 2 quantifiable postdose PK samples during pregnancy and at least 1 quantifiable postpartum sample) over the study period.

Treatment groups and duration:

[figure not shown]
This study will include pregnant women who have decided to continue treatment with commercial CZP in accordance with their treating physician prior to participating in the study. Study participants will be responsible for obtaining and administering commercially available CZP under the care of their physician and according to the locally approved product label.

The total study duration for a study participant will be a maximum of 53 weeks (40 weeks gestation period and up to 13 weeks (± 3 days) postpartum).

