7 DISCONTINUATION OF STUDY MEDICATION AND PARTICIPANT DISCONTINUATION/WITHDRAWAL

7.1 Discontinuation of study medication

Administration of CZP is not dictated by this protocol; therefore there are no protocol-defined reasons a participant should permanently discontinue CZP treatment.

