7.2 Participant discontinuation/withdrawal from the study

Participants are free to withdraw from the study at any time, without prejudice to their continued care.

A participant may withdraw from the study at any time at her own request, or may be withdrawn at any time at the discretion of the investigator for safety, behavioral, compliance, or administrative reasons.

If the participant withdraws consent for disclosure of future information, the sponsor may retain and continue to use any data collected before such a withdrawal of consent.

If a participant withdraws from the study, she may request destruction of any samples taken and not tested, and the investigator must document this in the site study records.

See the Schedule of Activities (Section 1.3) for data to be collected at the time of study discontinuation and follow-up and for any further evaluations that need to be completed.

Participants should be withdrawn from the study if any of the following events occur:

1. Participant develops an illness that would interfere with her continued participation.
2. Participant is noncompliant with the study procedures or medications in the opinion of the investigator.
3. Participant takes concomitant medications that lead to study withdrawal as defined in this protocol (Section 6.5.2).
4. Participant withdraws her consent.

5. The sponsor or a regulatory agency requests withdrawal of the participant.
6. If the study participant has a spontaneous abortion, the study participant will be discontinued from the study and a postpartum sample will not be obtained.
7. If the study participant ceases CZP during pregnancy, and upon restarting after delivery does not take CZP for at least 12 weeks and provides a PK sample within the window defined in Section 7.1.1, the study participant will be discontinued from the study.
8. If the study participant is given a dose of CZP exceeding 400mg Q2W, the study participant will be discontinued from the study.

Study participants should consult with their treating physician to determine the best method of ceasing administration of CZP based on recommendations located on the manufacturer's label.

Investigators should contact the Medical Monitor, whenever possible, to discuss the withdrawal of a participant in advance.

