- The investigator is obligated to perform or arrange for the conduct of supplemental measurements and/or evaluations as medically indicated or as requested by UCB to elucidate the nature and/or causality of the AE or SAE as fully as possible. This may include additional laboratory tests or investigations, histopathological examinations, or consultation with other health care professionals.
- An AE should be followed until it has resolved, has a stable sequelae, the investigator determines that it is no longer clinically significant, or the participant is lost to follow up. This follow-up requirement applies to AEs, SAEs, and AEs of special interest.
- If a participant dies during participation in the study or during a recognized follow-up period, the investigator will provide UCB with a copy of any post-mortem findings including histopathology.
- New or updated information will be recorded in the originally completed eCRF.
- The investigator will submit any updated SAE data to UCB within 24 hours of receipt of the information.

Reporting of SAEs

SAE Reporting to UCB via an Electronic Data Collection Tool

- The primary mechanism for reporting an SAE to UCB will be the electronic data collection tool.
- If the electronic system is unavailable for more than 24 hours, then the site will use the paper SAE data collection tool (see next section).
- The site will enter the SAE data into the electronic system as soon as it becomes available.
- After the study is completed at a given site, the electronic data collection tool will be taken off-line to prevent the entry of new data or changes to existing data.
- If a site receives a report of a new SAE from a study participant or receives updated data on a previously reported SAE after the electronic data collection tool has been taken off-line, then the site can report this information on a paper SAE form (see next section) or to the medical monitor by telephone.
- Contacts for SAE reporting can be found in the section on **SERIOUS ADVERSE EVENT REPORTING**.

This document cannot be used to support any marketing authorization application and any extensions or variations thereof.
PUBLIC COPY

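### After discontinuation for a dose above 400mg Q2W, routine AE collection ends 30 to 40 days after the last visit, while the overdose section sets at least 70 days of monitoring

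*Protocol*

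**What the plan says.** The discontinuation rule is Protocol 7.2 item 8: "If the study participant is given a dose of CZP exceeding 400mg Q2W, the study participant will be discontinued from the study". It removes her from the study, not from the drug. Section 7.1 says that "there are no protocol-defined reasons a participant should permanently discontinue CZP treatment".

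The Synopsis (1.1) fixes the last contact: "All study participants will be contacted via telephone for a SFU 5 weeks (± 5 days) after final study visit". It adds: "If any participant withdraws early, she will complete the SFU contact". SAP 3.2.2 likewise keeps the SFU for participants who discontinue. Neither document makes an exception for overdose. Table 1-1 (note i) and Protocol 8.3.1 collect AEs from consent to the SFU. Section 8.3.1 also has the investigator collect SAEs of any cause up to 35 (± 5) days after the final blood sample.

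Protocol 8.5 addresses the treating physician of an overdosed participant. Step 1 is to contact the Medical Monitor. Step 2 reads: "Closely monitor the participant for any AE/SAE and laboratory abnormalities until commercial CZP can no longer be detected systemically (at least 70 days"). Step 3 allows a PK sample "within 70 days from the date of the last dose of commercial CZP", if the Medical Monitor asks for one. Step 4 has the excess dose documented in the eCRF. The section also states: "Any SAE or nonserious AE associated with excessive dosing must be followed as any other SAE or nonserious AE".

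**The concern.** Section 8.5 treats 70 days as the minimum period in which events after an overdose deserve attention. The study's own collection can end well inside it for a woman who has exceeded the permitted maximum dose. Safety across pregnancy is a secondary objective, and the study runs no clinical safety laboratory tests (8.2.4), so reported events carry most of the safety information. An event that the treating physician sees after the SFU may have no route into the database.

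Two points in the text are also open. Step 2 of 8.5 gives no start for the 70 days. And 8.5 defines excessive dosing by the local label while 7.2 uses 400mg Q2W, so the protocol does not say whether a dose above 400mg Q2W is an overdose under 8.5.

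**Working it through.** **Inputs.** SFU at 5 weeks ± 5 days after the last visit (1.1, Table 1-1). SAE window of 35 ± 5 days after the final blood sample (8.3.1). Overdose monitoring of at least 70 days (8.5). Predose visits every 4 weeks in pregnancy. Predose postpartum visit (V5) at 12 ± 1 weeks after delivery.

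**The plan's own figure.** 5 × 7 = 35 days, and 35 ± 5 gives 30 to 40 days. This agrees with the SAE window in 8.3.1.

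**Assumptions.** A dose above 400mg Q2W is an overdose, and the 70 days run from that dose.

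**Formula.** Let s be the days from last visit to SFU (30 to 40), and d the days from the excess dose to the last visit (negative if the dose comes after it). Shortfall = 70 − (d + s), with a floor of zero.

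| Case | d | Smallest shortfall | Largest shortfall |
|---|---|---|---|
| Dose on the last visit day | 0 | 70 − (0 + 40) = 30 | 70 − (0 + 30) = 40 |
| Found at the next Q4W visit, which becomes the last visit | 0 to 28 | 70 − (28 + 40) = 2 | 70 − (0 + 30) = 40 |
| Illustration: dose 14 days after the last visit, no further visit | −14 | 70 − (−14 + 40) = 44 | 70 − (−14 + 30) = 54 |
| Dose after delivery, found at V5 | 0 to 91 | 0 | 70 − (0 + 30) = 40 |

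The shortfall is zero when d is at least 70 − s, that is 30 days if s = 40 and 40 days if s = 30. A 28-day interval cannot give that lag. The interval from delivery to V5 (77 to 91 days) can.

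**SAE window.** Scheduled visits in the sampling period include a blood sample, so this window normally ends with the SFU. A step 3 sample can move it. If the final blood sample is taken x days after the excess dose, the window ends on day x + 30 to x + 40: day 70 to 80 for x = 40, and day 100 to 110 for x = 70.

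**What stays open after the SFU.**
- SAEs that the investigator thinks may be associated with CZP have no time limit (8.3.1).
- Appendix 3 (10.3) provides for later reports with no causality limit: "If a site receives a report of a new SAE from a study participant".
- AEs already identified are followed (8.5, 10.3).
- Pregnancy complications are reportable, and the investigator collects follow-up on the participant and neonate, generally for at least 12 weeks (84 days) after delivery (10.4). For a dose during a pregnancy that reaches delivery, this runs past day 70.

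What remains is new nonserious AEs that are not pregnancy-related and start after the SFU, and active solicitation of unrelated SAEs if no later PK sample is taken.

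**The case against.** The strongest reply is that the two instructions have different addressees. Section 8.5 tells the treating physician how to care for an overdosed patient on a commercial drug; 8.3.1 tells the investigator what to record. Clinical monitoring can reasonably outlast data capture. This stands: a reader might infer that the protocol contradicts itself, and it does not. But 8.5 already ties the physician to the study through the Medical Monitor and the eCRF, and gives no clear route for new nonserious events after the SFU.

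A second reply is that 8.3.1 includes posttreatment periods that the protocol requires, which might cover the 70 days. That wording concerns events occurring during the study and sits within a window that ends at the SFU. She has by then been discontinued. It leaves the matter unclear rather than settled.

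A third reply is that the shortfall depends on an unstated start date and varies with timing. That is correct, and the figures hold only under the stated assumptions. A reader might also infer that the gap can reach the full 70 days. That would place the SFU on or before the very dose that triggers discontinuation. Even 68 days (dose 28 days after the last visit, s = 30) needs the call only two days after the dose. No upper limit is therefore claimed for that case.

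**Conclusion.** The point holds as a minor gap in safety capture. Under the two assumptions, routine collection ends 30 to 40 days before the 70-day minimum when the dose falls on the last visit day, and 2 to 40 days before it when the dose is found at the next Q4W visit. It ends earlier still when the dose follows the last visit and no further visit takes place. There may be no gap when the dose is found at V5. If a dose above 400mg Q2W is not an overdose under 8.5, the 70 days do not apply to her and only the unclear definition remains.

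A reader might infer that safety reporting stops altogether, or that serious events are lost. The documents do not support that, given the routes that stay open. The case should be rare among about 20 enrolled women, safety is summarized descriptively, and the PK analysis is unaffected. The reason to act is that the change is cheap and concerns the women with the highest dosing.

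**What to change.** In Protocol 8.5, state that a dose above 400mg Q2W is handled as an overdose, and that the 70 days start at the excess dose that led to discontinuation. That is a fixed date, so the period ends even if she stays on CZP or high dosing continues. Starting from the last dose of any kind would leave the end open in those cases.

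In 8.3.1 and Table 1-1, state that for such a woman the final telephone contact and AE/SAE collection take place at the later of the scheduled SFU and 70 days after that dose.

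The cost is a few sentences and a later telephone contact for the few women affected, with no new procedure. The call moves by the size of the shortfall, for example 30 to 40 days if the dose falls on the last visit day. Close-out could be delayed briefly if one of them is the last participant. SAP 3.8 already treats every AE as treatment-emergent, so the added events need no new rule for that classification.

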8.6 Pharmacokinetics

Plasma and whole blood samples of approximately 5mL will be collected for measurement of plasma concentrations of CZP as specified in the Schedule of Activities (Section 1.3). Samples may be collected at additional time points during the study, if warranted and agreed upon between the investigator and the Sponsor. Instructions for the collection and handling of biological samples will be provided by the Sponsor. The actual date and time (24-hour clock time) of each sample will be recorded.

Samples will be used to evaluate the PK of CZP. Each plasma sample will be divided for PK and immunogenicity analyses. Samples collected for analyses of CZP plasma concentration may also be used to evaluate safety or efficacy aspects related to concerns arising during or after the study.

